3.3.2 Exclusion Criteria

Target Disease Exceptions

- 1) History of diabetes insipidus
- 2) Symptoms of poorly controlled diabetes that would preclude participation in this trial including, but not limited to, marked polyuria and polydipsia with greater than 10% weight loss during the 3 months prior to enrollment, or other signs and symptoms.
- 3) History of diabetic ketoacidosis or hyperosmolar nonketotic coma.

Medical History and Concurrent Diseases

CV/Vascular Diseases:

- 4) History of malignant or accelerated hypertension.
- 5) Known or suspected secondary hypertension.

Any of the following CV/Vascular Diseases within 6 months of the enrollment visit:

- 6) Myocardial infarction.
- 7) Cardiac surgery or revascularization (coronary artery bypass surgery [CABG]/ percutaneous transluminal coronary angioplasty [PTCA]).
- 8) Unstable angina.
- 9) Unstable congestive heart failure (CHF).
- 10) CHF New York Heart Association (NYHA) Class III or IV. (see Appendix 1)
- 11) Transient ischemic attack (TIA) or significant cerebrovascular disease.
- 12) Unstable or previously undiagnosed arrhythmia.

Metabolic Diseases

13) History of Gout

Renal Diseases

- 14) History of unstable or rapidly progressing renal disease.
- 15) Conditions of congenital renal glucosuria.
- 16) Renal allograft

Hepatic Diseases

- 17) Significant hepatic disease, including but not limited to, chronic active hepatitis and/or severe hepatic insufficiency.
- 18) Documented history of hepatotoxicity with any medication.
- 19) Documented history of severe hepatobiliary disease.

Hematological and Oncological Diseases/Condition

- 20) History of hemoglobinopathy, with the exception of sickle cell trait (SA) or thalassemia minor; or chronic or recurrent hemolysis.
- 21) Donation of blood or blood products to a blood bank, blood transfusion, or participation in a clinical study requiring withdrawal of > 400 mL of blood during the 6 weeks prior to the enrollment visit.
- 22) Malignancy within 5 years of the enrollment visit (with the exception of treated basal cell or treated squamous cell carcinoma of the skin).
- 23) Known immunocompromised status, including but not limited to, individuals who have undergone organ transplantation or who are positive for the human immunodeficiency virus.

Central Laboratory Test Findings at Enrollment

- 24) Aspartate Aminotransferase (AST) > 3X Upper limit of normal (ULN).
- 25) Alanine aminotransferase (ALT) \geq 3X ULN.
- 26) Serum total bilirubin (TB) ≥ 1.5X ULN
- 27) Serum Creatinine (S_{Cr}) ≥ 2.0 mg/dL unless subject is on metformin then the exclusionary limits will be $S_{Cr} \geq 1.50$ mg/dL (133 mmol/L) for male subjects; $S_{Cr} \geq 1.40$ mg/dL (124 mmol/L) for female subjects
- 28) Estimated creatinine clearance (Crcl) of < 50ml/min
- 29) Hemoglobin ≤ 10.0 g/dL (100 g/L) for men; hemoglobin ≤ 9.0 g/dL (90 g/L) for women.
- 30) Creatine kinase (CK) \geq 3X ULN.
- 31) Positive for hepatitis B surface antigen.
- 32) Positive for anti-hepatitis C virus antibody.
- 33) Abnormal free T4 value.

Note: Abnormal thyroid stimulating hormone (TSH) value at enrollment will be further evaluated by free T4. Subjects with abnormal free T4 values will be

excluded. A one-time retest may be allowed, as determined by the Investigator, after a minimum of 6 weeks following the adjustment of thyroid hormone replacement therapy in subjects who have had a prior diagnosis of a thyroid disorder and who are currently receiving thyroid replacement therapy. Such cases should be discussed with the Sponsor prior to re-testing. The subject must have all enrollment procedures and laboratory assessments performed as part of this re-test, and all of these must meet enrollment eligibility criteria. The subject's number will however remain the same as initially assigned.

Allergies and Adverse Drug Reaction

34) Allergies or contraindication to the contents of dapagliflozin tablets.

Other Exclusion Criteria

- 35) Obesity that would limit accurate blood pressure measurement
- 36) History of bariatric surgery or lap-band procedure.
- 37) Administration of sibutramine, phentermine, rimonabant, benzphetamine, diethylpropion, methamphetamine, orlistat, and/or phendimetrazine.
- 38) Prisoners or subjects who are involuntarily incarcerated
- 39) Subjects who are compulsorily detained for treatment of either a psychiatric or physical (eg, infectious disease) illness
- 40) Replacement or chronic systemic corticosteroid therapy, defined as any dose of systemic corticosteroid taken for > 4 weeks within 3 months prior to enrollment visit.

NOTE: Topical or inhaled corticosteroids are allowed.

Eligibility criteria for this study have been carefully considered to ensure the safety of the study subjects and to ensure that the results of the study can be used. It is imperative that subjects fully meet all eligibility criteria.

Randomization Criteria:

Prior to randomization (first dose of double-blind study medication), the following criteria **MUST** be met:

- Subjects must have inadequately controlled hypertension, defined as SBP ≥ 140 and < 165 mmHg AND DBP ≥ 85 and < 105 mmHg, each representing the mean of three consecutive determinations, evaluated at both the enrollment and Day 1 visits.
- All non-central laboratory-related selection criteria evaluated at the enrollment visit
 have been met and have continued to be met throughout the lead-in period, and up to

the randomization visit. Central laboratory values that meet selection criteria at the enrollment visit are not required to meet the selection criteria at the entry into lead-in Day -28 visit. However, in the event of new laboratory abnormalities noted at the entry into lead-in Day -28 visit, the Investigator should ensure that they do not represent new and significant comorbidity that would preclude safe participation in the protocol. Such cases should be discussed with the medical monitor.

- No clinical conditions or clinically significant abnormalities, in any laboratory value(s) collected after enrollment and prior to randomization and/or ECG, which, in the Investigator's judgment, should preclude entry into the treatment period.
- Subjects should demonstrate good compliance with the administration of study medication (≥ 70% and ≤ 130%) during the lead-in period. For subjects with a compliance between ≥ 70% AND < 80% or > 120% AND ≤ 130%, the Investigator should ensure that there are no systematic factors that may result in unacceptable compliance with study medication during the treatment period of the trial. Such cases should be discussed with the Medical Monitor prior to randomization.
- Subjects should demonstrate the ability to perform SMBG as required per protocol (see Section 5.3.1).
- The total daily dose of commercially available OAD medication has remained stable since the enrollment visit.
- The total daily dose of commercially available ACEI or ARB and an additional antihypertensive medication has remained stable since the enrollment visit.

3.3.3 Women of Childbearing Potential

Dapagliflozin BMS-512148

Women of childbearing potential include any female who has experienced menarche and who has not undergone successful surgical sterilization (hysterectomy, bilateral tubal ligation, or bilateral oophorectomy) or is not postmenopausal. Post menopause is defined as:

- Amenorrhea ≥ 12 consecutive months without another cause and a documented serum follicle stimulating hormone (FSH) level >35 mIU/mL
- Women with irregular menstrual periods and a documented serum follicle stimulating hormone (FSH) level > 35 mIU/mL
- Women on hormone replacement therapy (HRT)

Dapagliflozin MB102077 BMS-512148 Clinical Protocol

Women who are using oral contraceptives, other hormonal contraceptives (vaginal products, skin patches, or implanted or injectable products), or mechanical products such as an intrauterine device or barrier methods (diaphragm, condoms, spermicides) to prevent pregnancy, or are practicing abstinence or where their partner is sterile (eg, vasectomy) should be considered to be of childbearing potential.

3.4 Concomitant Treatments

3.4.1 Prohibited and/or Restricted Treatments

3.4.1.1 Prohibited Treatments

Once enrolled, subjects may not receive any of the following for the duration of the study:

- Insulin
- Any injectable anti-diabetic medications (including GLP-1 agonists and amylin)
- Any additional oral anti-diabetic medications (other than the stable OAD medication (s) the subject is taking as described in inclusion criterion No.3).
- Antihypertensive medications other than either ACEI or ARB (as described in inclusion criterion No.3) unless the subject meets the criteria for severe or sustained hypertension (as described in section 3.5.1) and is eligible for antihypertensive rescue medication).
- Treatment with any systemic corticosteroid therapy that will involve ≥ 5 days of therapy (inhaled and topical are allowed). The medical monitor should be consulted prior to beginning therapy with corticosteroids for subjects who require systemic corticosteroid treatment.
- Administration of sibutramine, phentermine, rimonabant, benzphetamine, diethylpropion, methamphetamine, orlistat, and/or phendimetrazine.

3.4.1.2 Restricted Treatments

The following can be administered provided the dose was stable prior to **enrollment** and is maintained stable for the duration of the study:

- Herbal/over-the-counter preparations:
 - St. John's Wort
 - Fenugreek
 - Flaxseed
 - Chromium
 - Ginseng
 - Natural agents marketed for lowering blood sugar such as AntibeticTM,
 AlphabeticTM, DiabeticsTM, DB-7TM, DiabeticaTM, DiabetiksTM, Diacomp[™], DiaViteTM, GlucoCareTM, GlucotizeTM, GlycoNaseTM, SugarMaxTM or Sugar LossTM.

3.4.2 Other Restrictions and Precautions

Subjects must comply with their prescribed dosing regimen to preserve study integrity and ensure subject safety.

Subjects should be cautioned that any new prescription, over-the-counter or herbal/nutritional therapies should be discussed thoroughly with the Investigator prior to initiation as concomitant use could result in alterations to their glycemic control and may place them at risk for significant hypoglycemic episodes.

- Subjects must make every attempt to adhere to the diet and exercise counseling (see Section 5.9.2) and to the protocol visit schedule (see Section 5.1.1).
- Women of child-bearing potential must immediately contact the Investigator if they suspect they might be pregnant and if they have changed or plan to change their birth control method (see Section 6.4).

3.5 Discontinuation of Subjects from Treatment

Subjects MUST discontinue investigational product (and noninvestigational product at the discretion of the investigator) for any of the following reasons:

• Withdrawal of informed consent (subject's decision to withdraw for any reason)

- Any clinical adverse event (AE), laboratory abnormality or intercurrent illness which, in the opinion of the investigator, indicates that continued participation in the study is not in the best interest of the subject
- Pregnancy (see section 6.4)
- Termination of the study by Bristol-Myers Squibb (BMS)
- Loss of ability to freely provide consent through imprisonment or involuntarily incarceration for treatment of either a psychiatric or physical (eg, infectious disease) illness
- Clinical signs and symptoms of hypotension which, in the opinion of the investigator, indicate a need for less aggressive blood pressure treatment than specified in the protocol
- Protocol-defined lack of glycemic control (see Section 3.5.2)
- Sustained elevated S_{Cr} (see Section 3.5.3)
- Protocol-defined major hypoglycemia episode or recurrent non-major hypoglycemia episodes (see Section 3.5.4)
- Sustained elevated liver safety abnormalities (see Section 3.5.5)
- Sustained elevated CK (see Section 3.5.6)
- Sustained hyponatremia (see Section 3.5.7).

All subjects who discontinue should comply with protocol specified follow-up procedures as outlined in Section 5. The only exception to this requirement is when a subject withdraws consent for all study procedures or loses the ability to consent freely (ie, is imprisoned or involuntarily incarcerated for the treatment of either a psychiatric or physical illness).

If a subject was withdrawn before completing the study, the reason for withdrawal must be entered on the appropriate case report form (CRF) page.

3.5.1 Guidelines for the addition of a supplemental antihypertensive medication to control Sustained or Severe Hypertension

Subjects will continue to receive their current stable dose of commercially available ACEI/ARB plus an additional anti-hypertensive medication throughout the study.

• Criteria for Sustained Hypertension:

If the subject's seated blood pressure, determined from the mean of 3 replicated measurements, is between 165-180 mmHg systolic and 105-110 mmHg diastolic at any visit following randomization, the subject should continue taking study drug and return for a repeat blood pressure check in 3 days. If the subject's blood pressure continues to be > 165/105 mmHg, the subject may be eligible to receive open-label antihypertensive rescue medication.

• Criteria for Severe Hypertension:

If the subject's seated blood pressure, determined from the mean of 3 replicated measurements, is > 180/110 mmHg at any visit following randomization, the subject may be eligible to receive open-label antihypertensive rescue medication.

Subjects that have sustained or severe hypertension (as defined above) at any post randomization visit during the double-blind treatment period may be eligible to receive open-label rescue medication. Rescue medication means the addition of an approved oral antihypertensive agent, used according to conventional standards of care, to treat hypertension which may therefore allow the subject to remain in the trial.

The rescue medication should be prescribed by the Investigator in accordance with the approved product label in the applicable country and will not be provided by the Sponsor.

All rescue decisions will be based on confirmed local measurements, and the Medical Monitor will be notified. BP rescue evaluations (seated, orthostatic and the 24 hour ABPM) will be performed, **prior to the first dose of rescue medication being administered.** A supplemental (unscheduled) visit eCRF will need to be completed to collect all BP rescue evaluations.

Note: If a subject needs rescue for hypertension, the ABPM done at time of rescue will be the last ABPM measurement for the study and will not be repeated 1 week prior to Week 12.

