3.5.2 Discontinuation Guidelines Due to Protocol-Defined Lack of Glycemic Control

Subjects will continue to receive their current stable dose of commercially available OAD throughout the study. No new anti-diabetic therapy will be added during the study. At any

time following randomization, subjects with lack of glycemic control (defined at a FPG of > 270 mg/dl (central lab result) confirmed by a second central lab FPG > 270 mg/dl within one week) will be discontinued from the study for safety reasons. At this time, the Sponsor will be notified, and the Week 12/ET visit performed (see Section 5.3.8.1). Subjects will not receive rescue medication for lack of glycemic control at any time during the study.

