6 ADVERSE EVENTS

An *Adverse Event (AE)* is defined as any new untoward medical occurrence or worsening of a pre-existing medical condition in a patient or clinical investigation subject administered an investigational (medicinal) product and that does not necessarily have a causal relationship with this treatment. An AE can therefore be any unfavorable and unintended sign (including an abnormal laboratory finding, for example), symptom, or

disease temporally associated with the use of investigational product, whether or not considered related to the investigational product.

Adverse events can be spontaneously reported or elicited during open-ended questioning, examination, or evaluation of a subject. (In order to prevent reporting bias, subjects should not be questioned regarding the specific occurrence of one or more AEs.)

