9.1 Compliance

9.1.1 Compliance with the Protocol and Protocol Revisions

The study shall be conducted as described in this approved protocol. All revisions to the protocol must be discussed with, and be prepared by, BMS. The investigator should not implement any deviation or change to the protocol without prior review and documented approval/favorable opinion from the IRB/IEC of an amendment, except where necessary to eliminate an immediate hazard(s) to study subjects. Any significant deviation must be documented in the CRF.

If a deviation or change to a protocol is implemented to eliminate an immediate hazard(s) prior to obtaining IRB/IEC approval/favorable opinion, as soon as possible the deviation or change will be submitted to:

- IRB/IEC for review and approval/favorable opinion
- Bristol-Myers Squibb
- Regulatory Authority(ies), if required by local regulations

Documentation of approval signed by the chairperson or designee of the IRB(s)/IEC(s) must be sent to BMS.

If an amendment substantially alters the study design or increases the potential risk to the subject: (1) the consent form must be revised and submitted to the IRB(s)/IEC(s) for review and approval/favorable opinion; (2) the revised form must be used to obtain consent from subjects currently enrolled in the study if they are affected by the amendment; and (3) the new form must be used to obtain consent from new subjects prior to enrollment.

If the revision is an administrative letter, investigators must inform their IRB(s)/IEC(s).

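### After randomization no blood pressure level requires rescue or discontinuation, and the rescue criteria join systolic and diastolic limits, so a reading such as 170/100 mmHg meets neither

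*Supplement*

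**What the plan says.** Protocol Section 3.5.1 sets two blood pressure criteria after randomization, each on the mean of three seated readings.

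- **Sustained:** pressure "is between 165-180 mmHg systolic and 105-110 mmHg diastolic at any visit following randomization". The subject continues study drug and is rechecked in 3 days. If pressure is still above 165/105, rescue is permitted.
- **Severe:** pressure "is > 180/110 mmHg at any visit following randomization, the subject may be eligible to receive open-label antihypertensive rescue medication".

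Section 3.5.1 adds: "All rescue decisions will be based on confirmed local measurements, and the Medical Monitor will be notified". Seated, orthostatic and 24-hour ambulatory measurements come before the first rescue dose.

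Section 3.4.1.1 prohibits antihypertensives beyond the background regimen "unless the subject meets the criteria for severe or sustained hypertension (as described in section 3.5.1) and is eligible for antihypertensive rescue medication". Sections 3.1.3 and 4.3.1 hold background doses fixed.

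The list of mandatory discontinuations in Section 3.5 names hypotension but not hypertension. Its general item covers "Any clinical adverse event (AE), laboratory abnormality or intercurrent illness which, in the opinion of the investigator", makes continuing contrary to the subject's interest.

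**The concern.** Subjects enter this trial with uncontrolled hypertension despite two drug classes, and after Amendment 08 half of new subjects receive placebo. A rescue rule there should say plainly who may be treated and what happens at a dangerous level. Two things fall short.

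1. The consequence is permissive at every level. Nothing says that a subject above the severe limit is to be treated or withdrawn.
2. The criteria join systolic and diastolic pressure. A subject with a clearly high systolic but a moderate diastolic can miss both criteria, and Section 3.4.1.1 makes meeting one of them the condition for an added drug.

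What is at stake is the safety of individual subjects and uniform handling across sites. No bias in the primary comparison is claimed.

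**Working it through.** There is no stated figure in the plan to reproduce. The check applies the written criteria to sample readings.

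**Criteria as logic.** Sustained: 165 ≤ SBP ≤ 180 and 105 ≤ DBP ≤ 110. Severe, read two ways: SBP > 180 and DBP > 110, or SBP > 180 or DBP > 110.

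| Reading (mmHg) | Sustained | Severe, both needed | Severe, either enough |
|---|---|---|---|
| 170/107 | yes | no | no |
| 170/100 | no | no | no |
| 185/100 | no | no | yes |
| 200/109 | no | no | yes |
| 175/112 | no | no | yes |
| 185/112 | no | yes | yes |

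So 170/100 falls outside on any reading, because the sustained band is joined by an explicit 'and'. The 185/100, 200/109 and 175/112 cases depend on how the slash is read.

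**How the documents use the slash.** The Amendment 02 rationale writes the entry pressure as ≥ 140/85 mmHg. Sections 3.3.1 and 3.3.2 define that requirement as SBP ≥ 140 AND DBP ≥ 85. Within Section 3.5.1, the recheck limit of 165/105 follows a band joined by 'and'. Both favor the reading that needs both components.

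**Distance from entry.** Subjects may be randomized at up to just under 165/105. From 164/100, a systolic rise of 6 mmHg gives 170/100. That is 6/14 = 0.43 of the change SD of 14 mmHg assumed for the sample size.

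**Illustrative counts, placebo arm, n = 204 (Amendment 09).** Systolic and diastolic pressures were simulated jointly at enrollment, Day 1 and Weeks 2, 4, 8 and 12, in 32 scenarios. Subjects were selected on the entry limits at both enrollment and Day 1. Only the SD of 14 mmHg comes from the protocol. The assumed inputs are:

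- population mean SBP 143 or 148, mean DBP 56 lower;
- DBP SD 7 or 9;
- between-visit correlation 0.5 or 0.65;
- SBP-DBP correlation 0.4 or 0.6;
- further systolic shift 0 or -4, with half of that for diastolic.

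The ambulatory entry limit added by Amendment 02 is not modelled.

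| Event | Probability | × 204 |
|---|---|---|
| SBP > 180 at any visit | 0.0187-0.0600 | 3.8-12.2 |
| SBP > 180 and DBP > 110 at the same visit | 0.0004-0.0190 | 0.1-3.9 |
| SBP > 180 with DBP ≤ 110 at any visit | 0.0154-0.0553 | 3.1-11.3 |
| SBP > 180 or DBP > 110, one set of readings | 0.0233-0.1646 | about 5-34 |
| The same, confirmed at a repeat check | 0.0008-0.0289 | 0.2-5.9 |

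Of visits with SBP > 180, 68% to 98% have DBP ≤ 110. If both components are needed, the severe criterion would miss most of them. No count was made at the 165/105 level.

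**The case against.** The strongest reply is that the protocol leaves this to physicians and gives them the means.

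- **Backstops exist.** The discontinuation item quoted above rests on investigator judgment, and Section 6 defines an adverse event as "any new untoward medical occurrence or worsening of a pre-existing medical condition in a patient or clinical investigation subject", so worsening hypertension can qualify. Section 9.1.1 forbids unapproved deviations "except where necessary to eliminate an immediate hazard(s) to study subjects". Section 5.3.8.2 allows an unscheduled visit at any time. All of this stands and keeps the point minor.
- **The slash could mean either component.** Then 185/100 is severe and rescue is open. This stands as a possibility, though the documents' own usage points the other way, and it does not help 170/100.
- **Section 3.4.1.1 is loosely worded.** Read literally, it also bars the second background antihypertensive that inclusion criterion 3 requires, so sites may not apply it to the letter. That is fair, but loose wording is no reason to leave the rescue criteria unclear.

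Several stronger readings are tempting, and the documents do not support them.

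- A reader might infer that no pressure level requires any action. The 3-day recheck is an action, and rescue decisions need confirmation.
- A reader might see a contradiction with Section 1.5, which says discontinuation criteria for worsened hypertension exist. That sentence could refer to the Day -14 limit in the lead-in, and Amendment 08 updated Section 1.5 in wording that is not shown.
- A reader might take the mandatory stop for high glucose as proof of an oversight here. That rule has its own reason: "Subjects will not receive rescue medication for lack of glycemic control at any time during the study". Offering blood pressure rescue instead of withdrawal is a reasonable design.

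**Conclusion.** The point holds as a minor safety correction. After randomization no blood pressure level requires rescue or discontinuation. The joined criteria leave 170/100 outside both definitions on any reading, and 185/100 outside both on the more natural reading of the slash. If Section 3.4.1.1 is followed as written, such a subject cannot be given an added antihypertensive under the rescue rule, and only judgment-based routes remain.

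The conclusion rests on the wording. The simulated counts depend almost wholly on assumed inputs and do not estimate how many subjects would go untreated because of it.

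The text of Sections 3.5 and 3.5.1 available is that of the original protocol. The change lists of Amendments 02, 07, 08 and 09 show no repair; Amendment 02 lists Section 3.5.1 only for background-drug wording. Amendments 03-06 and the current consolidated protocol are not shown, so a later correction cannot be ruled out.

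**What to change.** Amend Section 3.5.1 as follows.

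1. **Sustained hypertension:** mean seated SBP > 165 OR DBP > 105 mmHg, confirmed at the 3-day recheck. Rescue stays at the investigator's discretion.
2. **Severe hypertension:** mean seated SBP > 180 OR DBP > 110 mmHg, confirmed as Section 3.5.1 already requires for rescue decisions.
3. **Consequence of confirmed severe hypertension:** the subject should receive rescue after the listed pressure evaluations, or be discontinued, in consultation with the Medical Monitor, with an early recheck (for example the protocol's own 3 days).

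With this, 170/100 can qualify as sustained and 185/100 as severe, and the exception in Section 3.4.1.1 then applies to both. The OR wording is the essential part. Item 3 is more a matter of judgment, and items 1 and 2 stand without it.

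The cost is a few sentences in one amendment. On the assumed inputs, about 5 to 34 of 204 placebo subjects would need a confirming measurement at the severe limit, and about 0 to 6 would be confirmed if confirmation is at a repeat check. The number newly eligible at the lower limit was not estimated and cannot be smaller than the number confirmed at the severe limit, though rescue there remains optional. Under Section 8.3 as shown, pressures after rescue do not count toward the blood pressure endpoints, so each extra rescue removes that subject's later values. Investigator discretion above the severe limit is slightly reduced.
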